#### **4.5. METHODOLOGY:**

##### **4.5.1. RECRUITMENT**

- Patients from either the outpatient department of CALHN public hospitals (Royal Adelaide and Queen Elizabeth Hospitals), or in the private consulting rooms of [name], [name], [name] or [name] (specialist weight loss surgeons), to be worked up for primary weight loss surgery will be invited to take part in the study
- If the patient meets the inclusion/exclusion criteria, the study will be discussed with the patient by their treating surgeon or member of the investigative team, and they will be provided with a pack containing:
  - A 'Participant Information Sheet' (Appendix 1)
  - A 'Participant Consent Form' (Appendix 2)
  - A 'Participant Details Form' (Appendix 3)
  - A 'GerdQ - Gastro-oesophageal reflux symptom questionnaire' (Appendix 4)
- If the potential participant would like further time to consider involvement, a follow-up meeting with a member of the investigative team will be arranged
- No financial inducement will be offered, however support for parking cost reimbursement will be offered

##### **4.5.2. PRE-SURGICAL WORK UP**

- Participants will undergo the following investigations pre-operatively:
  - Endoscopy, including:
    - Gastric (+/- oesophageal) biopsies
    - Gastric aspirates for biochemical analysis
  - Blood testing

- Complete blood examination
- Serum levels of glucose and HbA1c
- Quantification of fasting lipids
- Weight and height will be measured for body mass index
  - Hip and waist circumference will also be measured to evaluate central obesity index

#### 4.5.3. SURGERY

- Determination of the type of operation (LSAGB vs LSG vs LRYGB) to be performed will be at the discretion of the treating surgeon and informed patient preference.
- The operations will be performed by consultant oesophagogastric surgeons at the Royal Adelaide Hospital, The Queen Elizabeth Hospital, Western Hospital, Burnside War Memorial Hospital, Calvary Wakefield Hospital, Flinders Private Hospital or Ashford Hospital.

#### 4.5.4. POSTOPERATIVE CARE

- As per standard in-hospital pathways for clinical care following bariatric surgery

#### 4.5.5. FOLLOW-UP

- Participants will be contacted 4-6 weeks post-operatively to assess recovery and confirm continued participation in the study
- Participants invited at 6 months post-operatively to complete the same GerdQ Questionnaire (Appendix 4), in addition to a 'Investigations Tolerability Questionnaire' (Appendix 5)
- Participants who **have not had previous gallbladder surgery** will be invited to undergo the following investigations at 6 months post-operatively:
  - HIDA scan
    - To be performed at the Royal Adelaide Hospital in the Nuclear Medicine Department
    - Biliary scanning will be performed in all subjects following a 6-hour period of fasting and 24-hour abstinence from opiate containing medicine
    - Patients will be injected intravenously with 180 MBq 99mTc DIDA and then dynamic scans will be performed for 100 minutes on a GE, discovery D670 gamma camera using a LFOV with the patient lying supine on the scanning bed
    - A lipid-rich 'fatty meal' (60mL of *Calogen*) will be ingested orally after 30 minutes to stimulate gallbladder emptying

- Following this a SPECT CT scan will be performed of the abdomen for more accurate anatomical localization of activity
    - Delayed imaging may be performed depending on biliary function but only a single low-dose CT will be performed.
  - Endoscopy
    - Gastric (+/- oesophageal) biopsies
    - Gastric aspirates for biochemical analysis
  - Blood testing
    - Complete blood examination
    - Serum levels of glucose and HbA1c
    - Quantification of fasting lipids
  - Weight and height will be measured for body mass index
    - Hip and waist circumference will also be measured to evaluate central obesity index
- Participants who **have undergone previous gallbladder surgery** will only undergo the HIDA scan and symptom questionnaire.
- At 6 months after surgery, if a patient experiences clinically troublesome symptoms and a deterioration in symptom score is noted, then the patient will be offered oesophageal manometry and pH-impedance testing to evaluate swallowing function and to assess the presence of reflux in the oesophagus.

# 5. Outcomes

## 5.1. PRIMARY OUTCOMES:

- Scintigraphic evaluation of presence and degree of gastro-oesophageal bile reflux
- Impedance-based characterisation of oesophageal acidity, composition, duration and extent of oesophageal reflux
- Determination of presence of bile acids in gastric pouch and oesophageal fluid aspirates
- Determination of bile-acid induced gastric and oesophageal histological tissue changes

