#### 2.4. RESEARCH QUESTIONS

- Do LSAGB, LRYGB and LSG increase the incidence or amount of bile refluxing into the stomach and oesophagus?
- What is the patient tolerability of hepatobiliary scintigraphy and oesophageal impedance testing?

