## 6.2. FUNDING CONSIDERATIONS

- Costs of manometry and pH-impedance testing
  - These routine diagnostic tests, where performed post-operatively, will be performed and billed in accordance with clinical practice for ambulatory outpatient procedures
- Costs of hepatobiliary scintigraphy
  - These costs will be absorbed by the Royal Adelaide Hospital Department of Nuclear Medicine
- Cost of follow-up endoscopy
  - Follow up endoscopy will be performed to ensure that patients have not developed a hiatal hernia as a result of operative manipulation. In all bariatric surgery there is manipulation of the proximal stomach and a hiatal hernia may occur, increasing the risk of post-operative reflux.

The study investigators have no financial interest in the outcome of the research project and are not receiving any support from a commercial company or other financial support. There are no conflicts of interest to declare.

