## 7.2. PRE-OPERATIVE WORKUP

The current standard pre-operative work-up for patients at the Royal Adelaide and Queen Elizabeth Hospitals is for biometric measurements (height, weight and BMI), endoscopy, routine blood testing and selective use of oesophageal manometry and 24-hour pH-impedance reflux testing. All cohorts in the study will undergo these standard investigations, with selective use of manometry and pH-impedance testing as described earlier.

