## 7.3. POST-OPERATIVE FOLLOW-UP

Post-operative follow-up investigations will be performed at 6-months post-operatively. This time frame will provide sufficient time for patients to recover from their operation and returned to their usual activities.

Standard follow-up investigations after bariatric surgery at the Royal Adelaide and Queen Elizabeth Hospitals are biometric measurements (height, weight and BMI), routine blood testing and assessment of symptoms.

In addition to the above standard follow-up, all participants of this study will undergo hepatobiliary scintigraphy to evaluate bile reflux. This investigation has been used previously to assess for reflux (see section 3 of this protocol) and has more recently been used to evaluate reflux after weight loss surgery (24). For the specific safety considerations regarding radiation exposure with hepatobiliary scintigraphy, see section 8 of this protocol.

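### Impedance is an unrestricted primary outcome, but the protocol offers the test at 6 months only to patients whose symptoms have worsened, so this endpoint cannot validly compare the full operation groups

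*Protocol*

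**What the plan says.** Protocol section 5.1 names four primary outcomes: scintigraphy, impedance, bile acids in aspirates, and histology. The impedance item reads "Impedance-based characterisation of oesophageal acidity, composition, duration and extent of oesophageal reflux" and carries no restriction on who contributes. Section 9 plans statistical analysis of the primary outcomes for the three operations, with parametric, non-parametric or proportion tests between groups.

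Section 4.5.5 sets out the 6-month investigations for participants without earlier gallbladder surgery: HIDA scan, endoscopy with biopsies and aspirates, bloods, and body measurements. Impedance is not on that list. It appears afterwards as a conditional step. The condition is "if a patient experiences clinically troublesome symptoms and a deterioration in symptom score is noted". Even when this is met, the test is not scheduled but left to acceptance of an offer: "then the patient will be offered oesophageal manometry and pH-impedance testing".

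Three other sections agree with the conditional reading:
- Section 7.2, on the pre-operative work-up, says all cohorts have the standard investigations "with selective use of manometry and pH-impedance testing as described earlier". The list in section 4.5.2 omits impedance.
- Section 6.2 says of manometry and impedance: "These routine diagnostic tests, where performed post-operatively, will be performed and billed in accordance with clinical practice for ambulatory outpatient procedures".
- Section 7.3 names the investigation added for everyone, and it is a different one: "all participants of this study will undergo hepatobiliary scintigraphy to evaluate bile reflux".

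Section 2.4 also asks "What is the patient tolerability of hepatobiliary scintigraphy and oesophageal impedance testing".

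**The concern.** A primary outcome compared between operations should be measured in the groups being compared, or at least be missing for reasons unrelated to its value. Here it is missing by rule, and the rule is a symptomatic result of the operation. Reflux without symptoms is not seen after surgery, and patients enter the tested set because they deteriorated. A comparison of operations within that set answers a different question from the one in section 2.4, which asks whether each operation increases reflux. Within-patient change does not rescue it, because pre-operative impedance is selective too.

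At stake is one of four primary outcomes, which would be reported as a comparison of operations when it describes a small group selected on outcome. A later analysis plan cannot recover measurements that the protocol does not collect.

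**Working it through.** **Step 1. Is impedance scheduled for all participants anywhere?**

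| Protocol section | What it provides for impedance |
|---|---|
| 4.5.2 Pre-surgical work-up | Not listed |
| 7.2 Pre-operative work-up | Selective |
| 4.5.5 Follow-up, 6-month list | Not listed |
| 4.5.5 Follow-up, last item | Offered if symptoms are troublesome and the score is worse |
| 6.2 Funding | Billed as clinical practice where done |
| 7.3 Post-operative follow-up | Only scintigraphy is added for all |
| 5.1 Primary outcomes | Primary, unrestricted |
| 9 Analysis | Primary outcomes compared across operations |

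No section schedules it irrespective of symptoms, and none limits the endpoint to tested patients. Being measured requires three things in sequence: troublesome symptoms, a worse score, and acceptance of the offer.

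**Step 2. How much missing data does the plan allow for?** Section 4.4 gives 72 participants, 24 per group, from Fisher's exact test with 5% versus 50%, 80% power, alpha 0.05, an inflation factor of 1.2 and 10% for loss. The figure reproduces:
- Two-sided exact power is 77.7% at 16 per group and 81.3% at 17, so 17.
- 17 × 1.2 = 20.4, rounded up to 21.
- 21 × 1.1 = 23.1, rounded up to 24.
- 24 × 3 = 72.

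The plan thus expects about 21 of 24 per group to be measured, or 21/24 = 87.5%. Impedance would reach that only if nearly everyone deteriorated and accepted testing. The calculation concerns the percentage of patients with bile reflux, so it shows the missing-data allowance only and says nothing about power for impedance.

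**Step 3. What does the selection do?** The documents give no share tested, so this is an illustration on assumptions. Let r be the true proportion with reflux, s1 the chance that a patient with reflux is tested, and s0 the chance for a patient without. The same s1 and s0 apply to each operation. Then:
- share tested = r·s1 + (1 − r)·s0
- reflux among those tested = r·s1 / share tested

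For s1 = 60% and s0 = 10%:
- r = 5%: share tested = 0.05 × 0.6 + 0.95 × 0.1 = 0.125, which is 3.0 of 24; reflux among tested = 0.03/0.125 = 24%.
- r = 50%: share tested = 0.5 × 0.6 + 0.5 × 0.1 = 0.35, which is 8.4 of 24; reflux among tested = 0.30/0.35 = 86%.

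| s1, s0 (assumed) | Tested of 24, r = 5% | Tested of 24, r = 50% | Reflux among tested | Difference (true: 45 points) |
|---|---|---|---|---|
| 60%, 10% | 3.0 | 8.4 | 24.0% vs 85.7% | 61.7 points |
| 50%, 20% | 5.2 | 8.4 | 11.6% vs 71.4% | 59.8 points |
| 80%, 10% | 3.2 | 10.8 | 29.6% vs 88.9% | 59.3 points |

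In each case both group rates are too high and the difference is overstated by 14 to 17 points. The distortion disappears only if s1 = s0, that is, if testing is unrelated to reflux. A trigger based on symptoms and a symptom score gives no reason to expect that. Reflux is treated as yes/no here for simplicity; the impedance measures are mostly quantitative, but the same selection acts on them.

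**The case against.** The strongest counter-argument is that the main question survives without impedance. The primary objective in section 2.2 concerns bile acids in the stomach and oesophagus, the sample size rests on bile reflux, and section 3.3 itself says impedance-pH monitoring does not detect bile directly. Scintigraphy, aspirates and biopsies are scheduled without a symptom trigger. All of this stands. It limits the damage to one endpoint, and it is also a reason for not keeping that endpoint as primary.

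A second argument is that selective testing is ordinary clinical practice. That is not disputed; the problem is the label primary and the planned comparison, not who is tested.

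Four stronger readings may tempt a reader, and the documents do not support them:
- **That an operation causing more reflux sends milder cases to testing.** Section 4.5.5 applies one trigger to all operations and says nothing about severity. In the illustration above, the worse operation's tested group has more reflux.
- **That power can be quantified.** No rate of symptomatic deterioration is given. A yes/no test on a handful of patients per group does not represent an endpoint described by acidity, composition, duration and extent.
- **That nobody has a baseline.** Section 7.2 allows selective pre-operative testing, so some patients may have one. What is missing is a systematic baseline.
- **That impedance tolerability should be dropped.** How tested patients tolerated the test is a legitimate descriptive question. It needs only a statement of whom it covers.

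**Conclusion.** The contradiction is real and follows from the text alone: section 5.1 with section 9 treats impedance as a primary comparison of the three operations, while section 4.5.5 collects it only after symptomatic deterioration and an accepted offer. The endpoint gives no valid comparison of the full operation groups and has no systematic baseline. A description of the patients who are tested remains possible.

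The size cannot be fixed from the documents because the share tested is not stated. The selection is present at any share short of all patients; the 14 to 17 point overstatement rests on the assumed testing rates. A reader might infer that the study cannot compare the operations at all. That goes too far, because the other three primary outcomes do not depend on this trigger.

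**What to change.** Reconcile sections 4.5.5 and 5.1 by changing the status of the outcome:
- Move impedance out of the primary outcomes in section 5.1.
- Report it as a descriptive finding in tested patients: numbers eligible under the section 4.5.5 trigger, offered and tested for each operation, with results listed and no between-operation test. Say in section 9 that the planned group comparisons do not cover it.
- Keep impedance tolerability in sections 2.3, 2.4 and 5.2, but state that it applies only to patients who were selectively tested.

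The cost is wording in these sections and one fewer primary outcome. Which patients receive impedance testing is a clinical matter that this change leaves as it is.

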## 5.2. SECONDARY OUTCOMES:

- Biliary gastritis/oesophagitis/other markers of mucosal inflammation in the stomach and oesophagus
- Weight Loss/BMI
- Metabolic changes
- Quality of life
- Operative time
- Rate of conversion from laparoscopic to open operative technique
- Post-operative surgical complications such as, anastomotic leak, infection, cardio-respiratory events, kidney injury, venous thromboembolism, and so on.
- Length of hospital stay
- Patient tolerability of investigations (hepatobiliary scintigraphy, oesophageal reflux tests and endoscopy with aspiration and biopsy), with regard to personal comfort prior to, during, and after the investigation.

# 6. Resource and Funding Considerations

## 6.1. RESOURCE CONSIDERATIONS

This project will be conducted using facilities in the Departments of Surgery at the Royal Adelaide, Queen Elizabeth and Calvary Wakefield Hospitals and Department of Nuclear Medicine at the Royal Adelaide Hospital and will be supported by existing departmental research funds.

## 6.2. FUNDING CONSIDERATIONS

- Costs of manometry and pH-impedance testing
  - These routine diagnostic tests, where performed post-operatively, will be performed and billed in accordance with clinical practice for ambulatory outpatient procedures
- Costs of hepatobiliary scintigraphy
  - These costs will be absorbed by the Royal Adelaide Hospital Department of Nuclear Medicine
- Cost of follow-up endoscopy
  - Follow up endoscopy will be performed to ensure that patients have not developed a hiatal hernia as a result of operative manipulation. In all bariatric surgery there is manipulation of the proximal stomach and a hiatal hernia may occur, increasing the risk of post-operative reflux.

The study investigators have no financial interest in the outcome of the research project and are not receiving any support from a commercial company or other financial support. There are no conflicts of interest to declare.

# 7. Ethical Considerations

## 7.1. STUDY DESIGN

Although a prospective, randomized controlled trial would provide scientific rigour, we have elected to undertake a cohort study. Individual patient factors significantly impact the type of weight loss operation offered by surgeons, due to potential long-term morbidity, and thus clinical equipoise is lacking for randomization. Involvement in the study will not impact on the type of operation offered and investigator bias will be minimised through informed patient consent after in-depth discussion about available treatment options.

## 7.2. PRE-OPERATIVE WORKUP

The current standard pre-operative work-up for patients at the Royal Adelaide and Queen Elizabeth Hospitals is for biometric measurements (height, weight and BMI), endoscopy, routine blood testing and selective use of oesophageal manometry and 24-hour pH-impedance reflux testing. All cohorts in the study will undergo these standard investigations, with selective use of manometry and pH-impedance testing as described earlier.

## 7.3. POST-OPERATIVE FOLLOW-UP

Post-operative follow-up investigations will be performed at 6-months post-operatively. This time frame will provide sufficient time for patients to recover from their operation and returned to their usual activities.

Standard follow-up investigations after bariatric surgery at the Royal Adelaide and Queen Elizabeth Hospitals are biometric measurements (height, weight and BMI), routine blood testing and assessment of symptoms.

In addition to the above standard follow-up, all participants of this study will undergo hepatobiliary scintigraphy to evaluate bile reflux. This investigation has been used previously to assess for reflux (see section 3 of this protocol) and has more recently been used to evaluate reflux after weight loss surgery (24). For the specific safety considerations regarding radiation exposure with hepatobiliary scintigraphy, see section 8 of this protocol.

## 7.4. RISKS / ADVERSE EFFECTS OF INVESTIGATIONS

### 7.4.1. HIDA SCINTIGRAPHY

HIDA scintigraphy is a routine diagnostic test in the Royal Adelaide Hospital and Queen Elizabeth Hospital and performed in the Department of Nuclear Medicine numerous times per week. HIDA is often used to assess gall-bladder emptying, however it has also been used previously to assess for bile reflux. The research protocol will use standard clinical practices for assessment of bile reflux.

The risk of radiation exposure is discussed in section 8 of this protocol. Exposure to the intravenous tracer may induce an allergic response, at which time the investigation will be aborted and immediate medical assistance sought. The prolonged supine positioning (100 minutes) may cause some back discomfort for patients. Those with pre-existing back pain will be counseled prior to the study and prescribed analgesia as appropriate.

#### **7.4.2. ENDOSCOPY**

Endoscopy is a routine diagnostic test in the Royal Adelaide Hospital and Queen Elizabeth Hospital and performed in the Gastrointestinal Investigation Unit daily. The research protocol will use the standard clinical practices for this procedure.

Some minor discomfort or gagging may occur during the procedure, which is minimised by the use of intravenous opioid analgesia and sedation (benzodiazepine) as per standard clinical practices. Some minor bleeding can occur after collection of gastric and oesophageal biopsies. Patients on blood thinners will be instructed not to take them for a period prior to the endoscopy, after consultation with the prescribing clinician.

#### **7.4.3. OESOPHAGEAL MAMOMETRY AND IMPEDANCE-PH TESTING**

Oesophageal manometry and impedance-pH testing are routine diagnostic tests in the Royal Adelaide Hospital and Queen Elizabeth Hospitals and performed in the Oesophageal Function Laboratory daily. The research protocol will use the standard clinical practices for this procedure.

As with routine diagnostic manometry and impedance testing, after a 6hr fast, topical nasal anaesthesia (5% co-phenylcaine) will be applied before passing trans-nasally the oesophageal motility catheter lubricated with water-based jelly (K-Y jelly). Some minor throat discomfort or gagging may occur as the catheter passes the pharynx, but once positioned, adaptation occurs and there

is minimal or no discomfort. Similarly, minor transient discomfort may be experienced with the withdrawal (removal) of the catheter.

## 8. Specific Safety Considerations

### 8.1. RADIATION EXPOSURE

The subjects will be exposed to a diagnostic dose of radiation relating to the performance of the  $^{99m}\text{Tc}$  DIDA scan and also a low-dose CT scan of the abdomen as part of the SPECT/CT study. A radiation safety report is attached and the calculations indicate that subjects will be exposed to a dose of 9.2mSv per study. Please see report for full details.

# 9. Analysis and Reporting of Results

## Sample analysis

- Gastric biopsies will be reviewed by a qualified histopathologist within SA Pathology to assess:
  - Markers of tissue inflammation
  - Markers of DNA damage
  - Presence of bile acids
- Gastric aspirates will be analysed in the appropriate means by SA Pathology to assess:
  - Presence of bile acids
  - Concentration of bile acids
  - Identification of individual bile acids

## 99mTc DIDA scan analysis of DGER

- The rate of Hepatobiliary excretion of tracer and amount of DGER will be calculated from the scans using dynamic imaging with region of interest calculations over the liver, duodenum, gastric remnant and oesophagus.

## Statistical Analysis of data

- Statistical analysis will be undertaken for the primary outcomes relating to the three types of bariatric surgery being utilised in current clinical practice using commercially available statistical programs in consultation with professional statistical advice from our Unit's established connection with a health research statistician.
  - Normally distributed data will be reported as mean  $\pm$  standard error of the mean and statistical comparisons between groups will be made using parametric statistical tests.
  - Data that is not normally distributed, will be analysed using non-parametric statistics with reporting of median (interquartile range) and comparisons by applying non-parametric statistical tests with post-hoc analysis for differences across the 3 surgical groups.
  - Proportionate data will be compared using tests such as a Fisher's exact test or  $X^2$  test.
- The results will be presented at a relevant scientific forum and subsequently be submitted for publication in a peer-reviewed medical journal.

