## 4.4. SAMPLE SIZE:

*A sample size of 72 (24 in each of the 3 study arms) is required to find a significant difference in percentages of patients with bile reflux following 3 different types of operations.*

This was determined using a *Fisher's Exact Conditional Test for Two Proportions*, assuming a power of 80% and  $\alpha=0.05$ . A difference of 45% between worst and best operation in terms of reflux was considered (5% vs 50%, which represents a 'best estimate' of bile reflux post-operatively due to lacking published data). Because there is clustering on surgeon in this data, an inflation factor (IF) was used to account for correlation within surgeon. Inflation

factor= $1 + (m-1)p$  where  $m$ =cluster size and  $p$ =intra-class correlation coefficient (ICC) (<https://www.newton.ac.uk/files/seminar/20110815152516051-152821.pdf>). So IF for 5 surgeons and ICC=0.05 is 1.2. An additional 10% was then added to account for loss to follow-up. N per group was then multiplied by 3 (3 operation groups) to give total sample size needed.

A further 24 participants, from 1 surgical arm of the main trial, who have previously undergone surgical gallbladder removal (an exclusion criterion for the main trial) will also be recruited. This subset will allow us to compare the impact of gallbladder removal on the rate and severity of bile reflux for 1 operation. This sub-group of patients will not be subjected to the entire study protocol outlined below. They will only undergo the HIDA scan and the symptom questionnaire, but not the endoscopy.

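### Section 9 summarises normal data by the standard error instead of the SD, and the tests it names leave out the surgeon clustering that section 4.4 assumes

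*Protocol*

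**What the plan says.** The analysis text is in protocol section 9, under the heading on statistical analysis of data. It applies to the primary outcomes of the three operations and has three rules.

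- Normal data: a mean with the "standard error of the mean and statistical comparisons between groups will be made using parametric statistical tests".
- Other data: "Data that is not normally distributed, will be analysed using non-parametric statistics with reporting of median (interquartile range"), with non-parametric tests and post-hoc comparisons across the three groups.
- Proportions: "Proportionate data will be compared using tests such as a Fisher's exact test" or a chi-squared test.

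None of the three rules mentions the surgeon. Section 4.4 does: "Because there is clustering on surgeon in this data, an inflation factor (IF) was used to account for correlation within surgeon". It takes five surgeons and an intra-class correlation of 0.05, and arrives at a factor of 1.2. The result is stated as "A sample size of 72 (24 in each of the 3 study arms) is required". Section 4.5.3 leaves the choice of operation to the treating surgeon and the informed patient.

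**The concern.** There are two separate problems, both in what section 9 states.

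**The summary statistic.** A standard error shrinks as the arm grows and says nothing directly about how much patients differ. Whether an outcome is shown with a measure of precision or a measure of spread would depend only on whether it was judged normal. This can reach primary outcomes. Section 5.1 includes the degree of scintigraphic reflux and the duration and extent of oesophageal reflux, and the scan analysis in section 9 calculates an amount of reflux. Any of these judged normal would carry a standard error.

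**The tests.** Section 4.4 treats patients of the same surgeon as correlated and pays for that with extra patients. Fisher's exact test and the ordinary chi-squared test assume independent patients, as do the usual two- and three-group tests for continuous data. An analyst who follows section 9 would produce standard errors and p-values that do not match the plan's own account of the data. The study is meant to inform judgements about the safety of the single-anastomosis bypass, so the stated uncertainty matters.

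**Working it through.** **Inputs.** From section 4.4: 24 per arm, 72 in total; 5% v 50%; 80% power; alpha 0.05; intra-class correlation (ICC) 0.05; five surgeons; inflation factor 1.2; 10% loss. Section 4.4 does not state whether the test is one- or two-sided; two-sided is assumed here.

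**1. The plan's own sample size.** Exact power of the two-sided Fisher test is 77.7% at 16 per group and 81.3% at 17, so 17 is the smallest adequate size.
- 17 × 1.2 = 20.4, rounded up to 21
- 21 × 1.10 = 23.1, rounded up to 24
- 24 × 3 = 72

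The stated figure reproduces.

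**2. Standard error against SD.** SEM = SD/√n, so SD/SEM = √n.
- n = 24: √24 = 4.90
- After 10% loss, 24 × 0.9 = 21.6: √21 = 4.58 and √22 = 4.69

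An unadjusted bar of ±1 SEM covers about 67% (t distribution, 23 degrees of freedom), so it is not a 95% interval either.

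**3. Clustering and a single arm mean.** The variance is multiplied by 1 + (m − 1) × ICC, where m is the number of patients per surgeon, and the standard error by the square root of that.
- Plan's factor: 1 + (5 − 1) × 0.05 = 1.20; √1.20 = 1.095
- 24 patients spread evenly over five surgeons, m = 4.8: 1 + 3.8 × 0.05 = 1.19; √1.19 = 1.09

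The ordinary SEM of an arm mean therefore needs to be about 10% larger.

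**4. Clustering and a difference between operations.** The answer depends on a fact the protocol does not give, so the cases below are assumptions. Each takes equal numbers per surgeon and compares the standard error of the difference with the one from an ordinary test.

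| Assumed spread of surgeons | Variance factor | Standard error factor |
|---|---|---|
| Every surgeon does both operations equally, with the same surgeon effect in each | 1 − 0.05 = 0.95 | 0.97 |
| Five different surgeons in each arm (m = 4.8) | 1.19 | 1.09 |
| Two different surgeons in each arm (m = 12) | 1 + 11 × 0.05 = 1.55 | 1.24 |
| One different surgeon in each arm (m = 24) | 1 + 23 × 0.05 = 2.15 | 1.47 |

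In the first row, shared surgeon effects cancel and the ordinary test is slightly conservative. In the other rows it is too optimistic. The third and fourth rows are extremes for illustration. The second would need ten surgeons for two arms, more than the five that section 4.4 assumes, and is shown only because it matches the plan's factor.

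**The case against.** **A labelled standard error is not a wrong number.** With n given, SD = SEM × √n. A reader might infer that the plan understates spread five-fold. The documents do not support that: the statistic is named openly, and the error arises only if someone takes the SEM for an SD. What stands is that it is the wrong descriptive choice and does not match the interquartile range beside it.

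**The analysis section is an outline.** It says tests such as these, to be chosen with statistical advice, and a statistical analysis plan may exist. The term parametric would even admit a model with a surgeon term. A reader might infer that results will be p-values only and count missing confidence intervals as a defect. Intervals are commonly left to an analysis plan, so their absence is not a finding; they appear below only as part of the remedy. Nor does the protocol say how the SEM will be calculated, so it cannot be said that the error bars will certainly ignore surgeon. What stands is that the tests actually named for proportions, Fisher's exact and chi-squared, assume independence, and that is the type of comparison on which the study is powered.

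**The effect is modest.** This is true for an arm mean. The larger factors in the table rest on assumed allocations and cannot be presented as the plan's error.

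**The reach is limited.** The SEM rule does not apply to proportions, and outcomes judged non-normal already get a median and interquartile range. BMI and metabolic changes are secondary outcomes (section 5.2), outside the stated scope of this text. This objection stands as a limit on scope.

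**Conclusion.** The point holds as a minor one with two parts. Section 9 fixes a measure of precision as the descriptive summary of normal data, about one fifth of the SD at 24 per arm (SD/4.9, or about SD/4.6 after 10% loss). Section 9 also names tests that assume independent patients, although section 4.4 says they are not independent. Under the plan's own factor, the standard error of a single arm mean is about 10% too small. For a difference between operations, neither the direction nor the size can be fixed from the protocol. It ranges from slightly conservative, if surgeons perform all operations evenly, to clearly too optimistic, if surgeons concentrate in particular arms.

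These sizes rest on the plan's ICC of 0.05 and on equal numbers per surgeon. A reader might go on to infer that the sample size is wrong. Nothing here supports that: 24 per arm reproduces from the stated inputs.

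**What to change.** 1. In section 9, replace the mean with standard error by mean (SD) for normally distributed data.
2. State that comparisons between operations will use a method that accounts for surgeon, for example one stratified by or adjusted for surgeon, for both proportions and continuous outcomes. Report each difference (a risk difference or a mean difference) with its 95% confidence interval.
3. Report how many patients each surgeon contributed to each operation, so that the extent of overlap can be seen.

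**Cost.** No further patients, visits or tests are needed, provided the operating surgeon is recorded for each patient. The first change is wording only. The second is a modelling decision to be taken with the study's statistician: there are few surgeons, so any estimate of between-surgeon variation will be imprecise, and intervals may be slightly wider. Where a surgeon performs only one operation, no method can separate surgeon from operation, and the report should state this as a limitation.
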